6.8. Concomitant Therapy

Any medications, treatments, or therapies that the participant is receiving at Baseline (Study Day 1) or receives during the study (Study Day 1 through end of study [EOS]) are considered concomitant therapy and will be collected and documented in the study CRF.

Documentation includes the name of the therapy, with the reason for use, the dates of administration including start and end dates, and dosage information including dose and frequency.

Prior medications are those medications taken before the first dose of study IMP. A medication that starts prior to first dose but continues after the first dose of study IMP is classified both in prior and concomitant medications. Any procedures performed from Day 1 through EOS are considered concomitant procedures and will be collected and documented in the study CRF.

The Medical Monitor must be contacted if there are any questions regarding concomitant or prior therapy.

For participants who enroll in the EUT period, new concomitant therapy for the period from the single-dose Study Day 30 follow-up until the enrollment in the EUT will be collected during participant's screening for the EUT.

7. DISCONTINUATION OF STUDY IMP AND PARTICIPANT DISCONTINUATION/WITHDRAWAL

7.1. Discontinuation of Study IMP

7.1.1. Single-dose Period

This is a single dose period; not applicable.

7.1.2. Optional Extended Use Treatment Period

If study drug is permanently discontinued, the participant will be encouraged to participate in their remaining study visits. See [Table 6](#) for data to be collected at the time of discontinuation of IMP and follow-up. If a participant discontinues the study and needs to be started on another PAH medication, the Investigator should contact the Medical Monitor.

7.2. Participant Discontinuation/Withdrawal from the Study

A participant may withdraw from the study at any time at his/her own request or may be withdrawn at any time at the discretion of the Investigator for safety, behavioral, or compliance reasons.

At the time of discontinuing from the study after study drug administration, if possible, an early discontinuation evaluation should be conducted to maximize participant safety. This final evaluation and the reason for participant withdrawal must be documented in the CRF.

The participant will be permanently discontinued both from the study drug and from the study at that time.

If the participant is discontinued from the study due to an SAE, the Investigator will follow the participant until the Investigator deems that the SAE has resolved or stabilized.

The Investigator may withdraw the participant from the study due to absence of a PD response to TPIP. Lack of expected pharmacological action per se will not be reported as an AE or SAE. Such instances will be captured in the PK and PD assessments.

If the participant withdraws consent for disclosure of future information, Insmed may retain and continue to use any data collected before such a withdrawal of consent.

If a participant withdraws from the study, he/she may request destruction of any samples taken and not tested, and the Investigator must document this in the site study records.

7.3. Lost to Follow Up

A participant will be considered lost to follow-up if he or she repeatedly fails to return for scheduled follow-up visits and is unable to be contacted by the study site.

The following actions must be taken if a participant fails to return to the clinic for a required study visit:

- The site must attempt to contact the participant and reschedule the missed visit as soon as possible and counsel the participant on the importance of

maintaining the assigned visit schedule and ascertain whether or not the participant wishes to continue in the study.

- Before a participant is deemed lost to follow up, the Investigator or designee must make every effort to regain contact with the participant (where possible, 3 telephone calls and, if necessary, a certified letter to the participant's last known mailing address or local equivalent methods). These contact attempts must be documented in the participant's medical record.
- Should the participant continue to be unreachable, he/she will be considered lost to follow-up and to have withdrawn from the study.
- Site personnel, or an independent third party, will attempt to collect the vital status of the participant within legal and ethical boundaries for all participants, including those who did not get study IMP. Public sources may be searched for vital status information. If vital status is determined as deceased, this will be documented and the participant will not be considered lost to follow-up. Insmed personnel will not be involved in any attempts to collect vital status information.

Discontinuation of specific sites or of the study as a whole are handled as part of Appendix 1 ([Section 10.1.13.2](#)).

8. STUDY ASSESSMENTS AND PROCEDURES

Study procedures and their timing are summarized in [Table 1](#), [Table 2](#), [Table 3](#), [Table 4](#), [Table 5](#), and [Table 6](#).

All screening evaluations must be completed and reviewed to confirm that potential participants meet eligibility criteria prior to scheduling the study RHC procedure and inpatient admission. The RHC procedure and inpatient admission must be scheduled for as soon as possible once the participant's eligibility for the study is confirmed by screening. The Investigator will maintain a screening log to record details of all participants screened and to confirm eligibility or record reasons for screening failure, as applicable.

Procedures conducted as part of the participant's routine clinical management (e.g., previous RHC, previous echocardiogram, previous 6MWD test) and obtained before signing of the ICF may be utilized for screening or Baseline purposes provided the procedures meet the protocol-specified criteria and were performed within the time frames defined in the inclusion and exclusion criteria in [Section 5](#).

For participants who do not elect to enter the EUT period, the maximum amount of blood collected from each participant over the duration of the study, including any extra assessments that may be required is expected to be approximately 140 mL and will not exceed 200 mL. Approximately 80 mL will be required for PK sampling over 48 hours and approximately 20 mL for biomarker sampling. Safety and screening blood samples will require approximately 20 to 30 mL. Blood loss from the RHC procedure is anticipated to be negligible.

For participants who do elect to enter the optional EUT period within the 30 day follow-up window in the single-dose period, there is no anticipated blood collection. For participants who elect to enter the optional EUT period after the 30 day follow-up in the single-dose period, Safety and screening blood samples will require approximately 20 to 30 mL. Blood loss from the RHC procedures is anticipated to be negligible.

Repeat or unscheduled samples may be taken for safety reasons or for technical issues with the samples at the Investigator's discretion.

At any time, the Investigator has the option to discontinue assessments for participant safety or tolerability reasons. Additional laboratory, PK, and/or hemodynamic assessments may be performed as deemed necessary for participant safety. Following completion of scheduled events, the Investigator has the option of continued laboratory and/or hemodynamic monitoring as deemed appropriate for participant safety. If, in the interest of participant safety, the Investigator omits scheduled assessments/procedures or performs additional assessments/procedures, the reason for doing so must be reported on the CRF as an AE in order to avoid a protocol violation.

8.1. Pharmacodynamic Assessments

The results of each individual participant's PD assessments will contribute to the dosing decision for the next participant ([Section 4.3](#)).

8.1.1. Required PD Assessments with RHC

PVR, CO, PAP (mean), RAP (mean), RVP, hemoglobin, and MVO₂ will be measured via the RHC at the time points indicated in the SoA ([Table 2](#)). Oxygen consumption is part of the MVO₂ calculation and may be measured or estimated at 125 mL O₂ per square meter (m²) of body surface area (BSA). These or other parameters may be optionally measured at other time points or omitted to ensure participant safety at the Investigator's discretion. If measurements are missed, or additional measurements are taken for safety purposes, the reason must be documented as an AE in the CRF.

Institutional procedures for insertion, care, monitoring, and removal of the RHC will be followed. Specific technique and procedures for measurement of PVR, CO, PAP, RAP, RVP, hemoglobin, oxygen consumption, and MVO₂ are provided in a separate Procedure Guide.

8.1.2. Required Non-invasive PD Assessments

Systemic blood pressure (mmHg) may be measured by inflatable cuff. Systemic blood pressure must include 3 values: systolic, diastolic, and mean arterial pressure. Arterial oxygen saturation (SpO₂, %) and heart rate (beats per minute) may be measured by pulse oximeter.

8.1.3. Resting Respiratory Gas Exchange Assessments

Specific measurements for resting respiratory gas exchange assessment include changes from Baseline in respiratory rate (breaths per minute), minute ventilation (mL per minute), carbon dioxide production (VCO₂, mL per minute), end tidal oxygen concentration (ETO₂, %), and end tidal carbon dioxide concentration (ETCO₂, %). The gas exchange parameters will be monitored at the same time points as the PD assessments in [Section 8.1.1](#) ([Table 2](#), [Table 4](#)). Specific instructions for resting respiratory gas exchange assessment procedures and measurements are provided in a separate Procedure Guide.

8.1.4. Transthoracic Echocardiogram Assessments

Transthoracic echocardiogram is to be performed at Baseline and during a 2-8 hour window following TPIP administration ([Table 4](#)). Specific instructions for echocardiographic procedures and measurements are provided in a separate Procedure Guide.

8.1.5. Pulmonary CT Scan

8.1.5.1. Single-dose Period

Pulmonary CT scanning to assess pulmonary vasculature and blood flow is scheduled for Baseline and during a 4-8 hour window following TPIP administration ([Table 4](#)). Specific requirements and instructions for pulmonary CT scanning and required parameters are provided in a separate Procedure Guide.

8.1.5.2. Optional Extended Use Treatment Period

An optional pulmonary CT scan may be performed at first visit (± 3 days) and at EUT Week 16 (± 3 days) in the optional EUT period, as indicated in [Table 6](#). The CT scan will be performed according to instructions provided by the CT scan vendor.

8.2. Safety Assessments

Evaluation of the safety and tolerability of single doses of TPIP in participants with PAH is the primary objective of this study. Planned time points for all safety assessments are provided in [Table 1](#) and [Table 2](#). The results of the individual participant's safety assessments during and after TPIP administration will contribute to the dosing decision for the next participant (Section [1.3.2](#)). Participants who elect to enter the optional EUT period will also be monitored for safety, as listed in [Table 6](#).

8.2.1. Physical Examinations

Screening: The physical examination must focus on those areas that determine the individual participant's eligibility to participate in the study and do so safely at the Investigator's discretion and will be documented accordingly.

Baseline: The physical examination must focus on the participant's fitness for the study procedures and TPIP administration.

Discharge: The physical examination must focus on the participant's fitness to be safely discharged to home from the inpatient setting. Special attention must be paid to assessment of any new or ongoing AEs.

Follow-up: The in-person physical examination must focus on participant safety and assessment of AEs that were ongoing at discharge or have occurred since discharge.

8.2.2. Vital Signs

8.2.2.1. Single-dose Period

Temperature, heart rate, respiratory rate, and blood pressure at screening and 48 hour post-TPIP administration follow-up will be per the Investigator's usual outpatient practice and documented accordingly.

Baseline and post-TPIP administration: Changes from Baseline in heart rate, respiratory rate, and systemic blood pressure are PD endpoints as well as safety variables and must be measured as specified ([Section 8.1](#)). Vital signs outside of PD endpoints will be monitored per the inpatient unit's usual practices.

8.2.2.2. Optional Extended Use Treatment Period

Changes in heart rate, respiratory rate, body temperature, and systemic blood pressure will be monitored as described in [Table 6](#). Vital signs will be measured at Extended Use

Screening/Baseline (EUT Day 1), EUT Week 2, EUT Week 3, EUT Week 5, EUT Week 10, and EUT Week 16 and at the Early Discontinuation visit, if appropriate.

8.2.3. Electrocardiograms

Screening: a single 12-lead ECG will be conducted per the Investigator's usual practice

Baseline: A single 12-lead ECG will be performed to ensure the participant's eligibility for the study ([Section 5.2](#)). Inpatient telemetry monitoring will be utilized per the unit's usual practice until the participant is discharged from the inpatient setting, but routine telemetry readings will not be collected as study data unless they pertain to a relevant AE.

48 hours post-TPIP administration follow-up: a single 12-lead ECG will be conducted per the Investigator's usual practice.

8.2.4. Clinical Safety Laboratory Assessments

See [Section 10.2 \(Table 7\)](#) for the list of clinical laboratory tests to be performed and the SoA ([Table 1](#), [Table 2](#), [Table 5](#), [Table 6](#)) for the timing and frequency. All clinical laboratory tests will be performed locally by the study site.

The Investigator must review the laboratory report, document this review, and record any clinically significant changes occurring during the study as an AE. The laboratory reports must be filed with the source documents.

Abnormal laboratory findings associated with the underlying disease are not considered clinically significant unless judged by the Investigator to be more severe than expected for the participant's condition.

All laboratory tests with values considered clinically significantly abnormal during participation in the study or within 7 days after TPIP dosing must be repeated at the Investigator's discretion, consistent with the participant's level of disease until the values return to normal or baseline or are no longer considered clinically significant by the Investigator or Medical Monitor.

- If clinically significant values do not return to normal/baseline within a period of time judged reasonable by the Investigator, the etiology must be identified, and Insmed notified.]
- All protocol-required laboratory tests, as defined in Section 10, Appendix 2, must be conducted in accordance with the laboratory manual and the SoA ([Section 1.4](#)).
- If laboratory values from non-protocol specified laboratory tests performed at the institution's local laboratory require a change in participant management or are considered clinically significant by the Investigator (e.g., SAE or AE or dose modification), then the results must be recorded.

8.2.5. Pregnancy Testing

8.2.5.1. Single-dose Period

Willingness of WOCBP to undergo serum or urine pregnancy testing is a study eligibility criterion. Pregnancy tests will be conducted at screening, baseline, and Study Day 30. WOCBP

participants will be provided a home pregnancy test kit with instructions to conduct and report test results at the Study Day 30 follow-up visit which is scheduled to be by telephone call or telemedicine. If the participant elects to enter the optional EUT period and the remote safety follow-up visit overlaps with the start of the EUT period, the results of a urine pregnancy test will be recorded at the first visit in the extended treatment period.

8.2.5.2. Optional Extended Use Treatment Period

Urine pregnancy tests will be performed in-clinic at EUT Baseline (EUT Day 1) in WOCBP. WOCBP participants will be provided home pregnancy test kits with instructions to conduct the pregnancy tests every 30 days or more if required during the treatment and follow-up periods. Study site personnel will contact the participant every 30 days by telephone and record the pregnancy test results. An additional on-site urine test must be performed prior to starting any procedure that requires the use of ionizing radiation.

8.3. Adverse Events (AEs), Serious Adverse Events (SAEs), and Other Safety Reporting

The definitions of AEs and SAEs can be found in Appendix 3.

AEs will be reported by the participant (or, when appropriate, by a caregiver, surrogate, or the participant's legally authorized representative). AEs may be solicited or unsolicited. Solicited and unsolicited AEs are defined in [Section 10.3](#).

The Investigator is responsible for detecting, documenting, and recording events that meet the definition of an AE or SAE as provided in the protocol and remain responsible for following up all AEs.

The Investigator should proactively follow participants with AEs until the EOS for each participant. At the EOS visit, the Investigator will record the AE status (stable or not stable) in the electronic CRF.

The method of recording, evaluating, and assessing causality of AEs and SAEs and the procedures for completing and transmitting SAE reports are provided in [Section 10.3](#).

8.3.1. Time Period and Frequency for Collecting AE and SAE Information

All AEs (serious and non-serious) for the core, single-dose period will be collected from the signing of the ICF until the Study Day 30 follow-up visit at the time points specified in the SoA ([Table 1](#), [Table 2](#)). Medical occurrences that begin after obtaining informed consent but before TPIP administration will be recorded as Medical History/Current Medical Conditions, not as AEs.

SAEs that occur after signing the ICF but before study IMP starts must be recorded and reported as SAEs. Non-serious medical occurrences that begin after obtaining informed consent but before TPIP administration will be recorded as Medical History/Current Medical Conditions, not as AEs.

For participants who enroll in the EUT period, AEs for the period from the single-dose Study Day 30 follow-up until the enrollment in the EUT will be collected during participant's screening for the optional EUT period. All AEs and SAEs for participants who choose to enroll in the optional EUT period will be recorded at the time points specified in the SoA ([Table 5](#), [Table 6](#)).

All SAEs will be recorded and reported to Insmed or designee immediately and under no circumstance must this exceed 24 hours, as indicated in Appendix 3, ([Section 10.3](#)). The Investigator will submit any updated SAE data to Insmed within 24 hours of it being available.

Investigators are not obligated to actively seek information on AEs or SAEs after conclusion of the study participation. However, if the Investigator learns of any SAE, including a death, at any time after a participant has been discharged from the study, and he/she considers the event to be reasonably related to the study IMP or study participation, the Investigator must promptly notify Insmed.

8.3.2. Method of Detecting AEs and SAEs

Care will be taken not to introduce bias when detecting AEs and/or SAEs. Open-ended and non-leading verbal questioning of the participant is the preferred method to inquire about AE occurrences.

8.3.3. Follow-up of AEs and SAEs

After the initial AE/SAE report, the Investigator is required to proactively follow each participant at subsequent visits/contacts. The Investigator should proactively follow participants with AEs until the EOS for each participant. All SAEs will be followed until resolution, stabilization, the event is otherwise explained, or the participant is lost to follow-up (as defined in [Section 7.3](#)). If a site receives a report of a new SAE from a study participant or receives updated data on a previously reported SAE after the electronic data collection tool has been taken offline due to study completion, then the site can report this information to the Medical Monitor by email or telephone.

8.3.4. Regulatory Reporting Requirements for SAEs

Prompt notification by the Investigator to Insmed of an SAE is essential so that legal obligations and ethical responsibilities towards the safety of participants and the safety of a study intervention under clinical investigation are met.

Insmed has a legal responsibility to notify relevant health authorities and regulatory agencies about the safety of a study drug under clinical investigation. This study is being conducted in the USA only; regulatory requirements relating to safety reporting to the US FDA, IRBs, and investigators will be followed.

An Investigator who receives an investigator safety report describing an SAE or other specific safety information (e.g., summary or listing of SAEs) from Insmed will review and then file it along with other study documents and will notify the IRB, if appropriate according to local requirements.

Investigator safety reports must be prepared for SUSARs according to local regulatory requirements and Insmed policy and forwarded to Investigators as necessary. No serious adverse

reactions are considered expected for TPIP. Please refer to the Reference Safety Information in Section 6.1 of the Investigator's Brochure.

8.3.5. Pregnancy

Details of all pregnancies that occur in WOCBP participants within 30 days after TPIP administration will be collected. Male participants with WOCBP partners must continue to use contraception for 90 days after TPIP administration and report any pregnancies that occur within that time period.

If a pregnancy is reported, the Investigator will record pregnancy information on the appropriate form and submit it to Insmed within 24 hours of learning of the pregnancy in a female participant or female partner of male participant and after obtaining the necessary signed informed consent from the female partner.

While pregnancy itself is not considered to be an AE or SAE, any pregnancy complication or elective termination of a pregnancy for medical reasons will be reported as an AE or SAE.

Abnormal pregnancy outcomes (e.g., spontaneous abortion, fetal death, stillbirth, congenital anomalies, ectopic pregnancy) are considered SAEs and will be reported as such.

Any female participant who becomes pregnant while participating in the study will be discontinued from the study.

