4.4. Study Completion

A participant will be considered to have completed the study if he/she has completed the Study Day 30 safety follow-up (shown in [Table 1](#)) and has not elected to enter the optional EUT period. A participant who has entered the optional EUT period will be considered to have completed the study if he/she has completed the EUT period safety follow-up (EUT Day 142). The study will be considered completed on the date of the last safety follow-up of the last participant in the study.

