10.3.4. Reporting of SAEs

All SAEs, regardless of causality, must be reported to the organization delegated by Insmed on a Serious Adverse Event Report Form within 24 hours of becoming aware of the event; corrections and additions are required to be submitted within 24 hours. Study-specific email, phone, and fax number for SAE reporting information will be provided to the study sites.

Unexpected drug related SAEs as assessed by Insmed or authorized person qualify for expedited reporting and will be reported to the IRB, regulatory authorities, participating Investigators and, if cross reporting is required for SUSARs, in accordance with all applicable global laws and regulations. A SUSAR is a Serious Adverse Reaction, which is suspected to be caused by the investigational medicinal product and which is unexpected; e.g., its nature or severity is not

consistent with the information in the relevant Reference Safety Information. SAEs, including those that do not meet requirements for expedited reporting, and all other AEs will be reported to the regulatory agencies as appropriate (e.g., for the FDA these are reported in the Investigational New Drug annual report and for the European Medicines Agency, these are reported in the Development Safety Update Report).

SAE Reporting to Insmed via an Electronic Data Collection Tool

The primary mechanism for reporting an SAE to Insmed will be the electronic data collection tool.

If the electronic system is unavailable, then the site will use the paper SAE data collection tool (see next section) to report the event within 24 hours.

The site will enter the SAE data into the electronic system as soon as it becomes available. After the study is completed at a given site, the electronic data collection tool will be taken off-line to prevent the entry of new data or changes to existing data.

If a site receives a report of a new SAE from a study participant or receives updated data on a previously reported SAE after the electronic data collection tool has been taken off-line, then the site can report this information on a paper SAE form (see next section) or to the Medical Monitor by email or telephone.

SAE Reporting to Insmed via Paper Data Collection Tool

Facsimile transmission of the SAE paper data collection tool is the preferred method to transmit this information to Insmed.

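### Amendment 1 says abnormal pregnancy outcomes will be reported as SAEs, but nothing it states requires a pregnancy to be followed to its outcome, and term outcomes in female participants fall after the last planned contact

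*Protocol*

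**What the plan says.** All references are to the Amendment 1 text unless stated otherwise.

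- Section 8.3.5 on outcomes: "Abnormal pregnancy outcomes (e.g., spontaneous abortion, fetal death, stillbirth, congenital anomalies, ectopic pregnancy) are considered SAEs and will be reported as such". Pregnancy itself is neither an AE nor an SAE.
- Section 8.3.5 on reporting a pregnancy: the Investigator completes a form and must "submit it to Insmed within 24 hours of learning of the pregnancy". No later update is mentioned. A participant who becomes pregnant is discontinued from the study.
- Section 8.3.5 on men: those with partners of childbearing potential must continue "contraception for 90 days after TPIP administration and report any pregnancies that occur within that time period".
- Section 4.4 on the end of participation: "A participant will be considered to have completed the study if he/she has completed the Study Day 30 safety follow-up" and has not entered the extended use treatment (EUT) period. A participant who did enter it has finished on having "completed the EUT period safety follow-up (EUT Day 142").
- Section 8.3.1 on later events: "Investigators are not obligated to actively seek information on AEs or SAEs after conclusion of the study participation". An SAE that the Investigator happens to learn of afterwards must be notified if "he/she considers the event to be reasonably related to the study IMP or study participation".
- Section 10.3.4 puts no such condition on SAEs: "All SAEs, regardless of causality, must be reported to the organization delegated by Insmed".
- Section 7.2 requires follow-up after discontinuation when the cause was an SAE. Section 8.3.3 follows AEs to the end of study and SAEs to resolution.

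**The concern.** Stillbirth and congenital anomaly are usually known only late in pregnancy or at birth. Section 8.3.5 says they will be reported, but no sentence makes anyone responsible for finding out. A site that follows the stated rules exactly would send the pregnancy form, discontinue the participant, perform the early discontinuation evaluation and stop. Because pregnancy is not an SAE, the SAE follow-up rules do not start with it. A partner is not a participant, so general AE follow-up does not clearly reach her at all.

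Whether a late outcome that does become known must also be judged related is left open: Section 8.3.1 says so, while Sections 8.3.5 and 10.3.4 do not.

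Amendment 1 adds 16 weeks of daily dosing, mostly at home, with pregnancy tests every 30 days for women of childbearing potential. A pregnancy would therefore probably be detected and then not tracked. The outcome of an exposed pregnancy cannot be recovered later if nobody was assigned to ask.

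**Working it through.** **The plan's own figures.** EUT participation is 16 × 7 + 30 = 142 days, as Section 4.1 states. The core period is 30 + 30 + 2 = 62 days, also as stated. The last planned contacts are Study Day 30 (± 2) and EUT Day 142 (± 3).

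**Assumption.** The documents give no time to delivery. I take birth at 37 to 40 weeks of gestation, which is 37 × 7 − 14 = 245 to 40 × 7 − 14 = 266 days after conception. Birth at 42 weeks (280 days) only lengthens the gaps.

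**Female participants.** Gap = conception day + 245 (or 266) − last contact day.

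| Conception | Last contact | Gap to birth (days) |
|---|---|---|
| EUT Day 1 | EUT Day 142 | 1 + 245 − 142 = 104, to 1 + 266 − 142 = 125 |
| EUT Day 112 | EUT Day 142 | 112 + 245 − 142 = 215, to 236 |
| Study Day 1, no EUT | Study Day 30 | 1 + 245 − 30 = 216, to 237 |

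At the latest permitted visits (Study Day 32, EUT Day 145) the smallest gaps are 246 − 32 = 214 and 246 − 145 = 101 days. Term would fall inside EUT participation only if conception came about 100 days before EUT Day 1, and the pregnancy test at EUT entry should exclude that. Discontinuation for pregnancy moves the last contact earlier still.

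**Partners of male participants.** The reporting window closes 90 days after the last dose:

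- single dose only: Study Day 91, which is 91 − 30 = 61 days after the last contact
- last dose EUT Day 112: EUT Day 202, which is 202 − 142 = 60 days after
- last dose EUT Day 126, after a two-week taper: EUT Day 216, which is 216 − 142 = 74 days after

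A conception at the end of these windows gives birth between 202 + 245 − 142 = 305 and 216 + 266 − 142 = 340 days after the last contact.

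**The exception.** Section 4.1.4 allows a gap of up to 6 months between the two periods. If a man starts the EUT g days after his single dose, his latest contact is Study Day g + 145. A partner who conceives on Study Day c reaches 37 weeks before that if c ≤ g − 100, which first becomes possible at g = 101. With g = 183 the latest contact is Study Day 328, and conceptions up to Day 328 − 245 = 83 (37 weeks) or 328 − 266 = 62 (40 weeks) reach term before it. No text requires the site to ask about the outcome at that contact.

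**Expected number.** Assume 6 to 10 participants, all of childbearing potential and all entering the EUT (an upper bound), contraceptive failure of 1 to 5% a year, and 30 + 142 = 172 days at risk. The expected number of participant pregnancies runs from 6 × 0.01 × 172/365 = 0.028 to 10 × 0.05 × 172/365 = 0.236. Abnormal outcomes would be fewer. Partner pregnancies are not counted.

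**The case against.** The strongest objections concern what is not in view. The pregnancy form is not shown and may have an outcome field, and collecting details of all pregnancies could be read to include the outcome. The file also opens with the closing appendices of another copy of the protocol whose Section 8.3.5 is missing. The document history lists only versions 1.0 and 2.0, so that copy may be a duplicate, but a different text cannot be ruled out. These limits stand. A field on a form due within 24 hours of learning of the pregnancy still creates no duty to follow up, and the Amendment 1 text that is shown contains none.

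Existing provisions also cover part of the ground: pregnancy complications and medical terminations are reportable, men have their own duty to report partner pregnancies, Section 7.2 calls for an early discontinuation evaluation, and any SAE already identified is followed to resolution. None of these reaches a term outcome.

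Some stronger readings are not supported:

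- A reader might infer that every partner outcome falls after the last contact. The late-EUT case above contradicts that.
- A reader might infer that the 60- to 74-day partner shortfall is general. It assumes dosing to EUT Day 112 or 126, or no EUT. A man who stops drug early and keeps attending visits has a smaller shortfall or none.
- A reader might treat the follow-up sentences in version 1.0 as evidence of an error in Amendment 1. A difference from superseded text is not an error, and the point rests on Amendment 1 alone.

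**Conclusion.** The point holds for the Amendment 1 text. Section 8.3.5 says outcomes will be reported, and the stated rules would let a site stop tracking an exposed pregnancy 100 or more days before term. Given the assumed 245 to 266 days from conception to birth, this applies to every term outcome in a female participant. It applies to most partner outcomes, except where a man enters the EUT about 100 or more days after his single dose.

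Priority is low: at most about a quarter of a participant pregnancy is expected under assumptions that overstate exposure. This is a gap in safety reporting. A reader might infer that the primary endpoint is affected, but treatment-emergent events are counted only to 28 days after the last dose (Section 10.3.1), long before term, and no such effect is claimed.

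**What to change.** Add one sentence to Section 8.3.5: *A pregnant participant, or a consenting pregnant partner of a male participant, and the neonate will be followed to pregnancy outcome, including after discontinuation and notwithstanding Section 8.3.1, and the outcome reported to the sponsor.*

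The follow-up sentences in Section 8.3.5 of protocol version 1.0 can serve as a wording model. Its sentences limiting post-study reports to related events, and excusing the Investigator from seeking them, should not be carried over.

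The cost is an outcome form and, rarely, telephone follow-up to delivery. Sample size, dosing rules and the schedule for other participants do not change.

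Optionally, pregnancy after first dosing could stop study drug while safety contacts continue to Study Day 30 or EUT Day 142. That would help only with early losses and complications, and the finding does not depend on it.
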